9.5. Site Documentation and Management

The following information will be maintained by the Principal Investigator:

- Delegation of Authority Log, indicating study role, training date, on-study date (date of first research-related procedure or scan), and off-study date
- Financial Disclosure Forms and updates
- Copies of all correspondence with the IRB of record, including all approval letters and approved template informed consent documents, in chronological order by date.
- Copies of all correspondence with the local Scientific Review Committee, including approval letters, renewals, and other types of communication.
- Study agent accountability log
- Serious adverse event (SAE) log, documenting the subject, date, event, relatedness, follow-up, and outcome, with dates of communication to the IRB of record and Oncore/CCTO-Safety (Stanford site).
- Log of Deviations (ie, excursions from the protocol not authorized by the Stanford investigator and approved by the IRB). The Log of Deviations must be maintained in OnCore.
- Laboratory documentation, including copies of local site CAP and CLIA certificates, State licenses, laboratory director CV and medical license, with laboratory normal values/reference ranges for all labs used in the study.

- Printed, dated copy of roster for IRB of record, for each year of the study.

9.6. FDA Oversight

9.6.1. Investigational New Drug (IND) Application Considerations

This study will be conducted under IND-164301, held by [name].

9.6.1.1. Protocol Amendments

The protocol will be conducted at all times according to the current version of the protocol as approved by the IRB of record. IRB-approved protocol versions will be submitted to the IND as a Protocol Amendment: Change in Protocol.

9.6.1.2. IND Reports

Information regarding the progress and status of this study will be submitted to IND-164301, in accordance to the content and format defined at [21CFR§312.32 \(Safety Reports\)](#) and [312.33 \(Annual Reports\)](#).

9.6.2. Investigational Device Exemption (IDE) Application Considerations

Exempted Device Investigation

This study describes the use of a device in a study that is considered to not require an Investigational Device Exemption (IDE), as elucidated at [21CFR§812.2\(c\)](#). This study will be submitted to the IRB of record, and their approval obtained, before the study is initiated.

10. STATISTICAL CONSIDERATIONS

10.1. Statistical Plan

This study is an open-label, single-arm, single-center, phase 2 study to assess the efficacy and safety of cryoablation and nirogacestat in desmoid tumors.

10.1.1. Method of Treatment Assignment

The interventional model is non-randomized.

10.2. Study Endpoints and Analyses

10.2.1. Primary Endpoint and Analysis

10.2.1.1. Primary Endpoint

The clinical benefit rate (CBR) is defined as the number and proportion of participants who are assessed with either a complete response (CR), a partial response (PR), or stable disease (SD) prior to 1 year after treatment start and show no evidence of loss of response nor progression

within that year. Response and progression will be assessed according to the Revised Response Evaluation Criteria in Solid Tumors (RECIST) v1.1.

10.2.1.2. **Primary Analysis Plan**

The primary analysis will be the calculation of the clinical benefit rate, (CBR), defined as the percentage of subjects in the analysis population who achieve a complete response (CR), partial response (PR), or stable disease (SD) as measured at 12 months \pm 1 month (approximately 1 year) from the start of treatment. CR, PR, and SD are as defined by RECIST v1.1. (See Appendix C RECIST v1.1). The CBR and the two-sided 95% Clopper-Pearson (exact) confidence interval will be calculated.

The analysis population will include all subjects who started nirogacestat and underwent cryoablation. Subjects who withdraw from the study prior to start of treatment or before receiving cryoablation and completing 1 year of treatment will be replaced.

10.2.1.3. **Relevant Subset for Primary Objective and Endpoint**

Evaluable subjects are those subjects who have received cryoablation therapy and completed 1 year of treatment.

10.2.1.4. **Primary Objective and Endpoint Assessment Methods**

CBR will be evaluated on the basis of clinical response as measured using imaging by MRI scan and evaluated by RECIST v1.1 (Appendix C). Determination of response will be made by the treating investigator.

10.2.1.5. **Measurement Time Points for Primary Objective / Outcome**

Imaging will be performed at screening, then every 3 cycles (ie, every 12 weeks \pm 14 days) until End of Treatment. MRI scan will be used at screening and at subsequent time points.

10.2.2. **Secondary Endpoints and Analysis**

10.2.2.1. **Clinical Benefit Rate (CBR) assessed by modified RECIST**

For tumors with MRI enhancement, CBR will be evaluated on the basis of clinical response as measured using imaging by MRI scan and evaluated by modified RECIST (Appendix D). Determination of response will be made by the treating investigator. Imaging will be performed at screening, then every 3 cycles (ie, every 12 weeks \pm 14 days) until End of Treatment. MRI scan will be used at screening and at subsequent time points.

10.2.2.2. **Median Progression-free Survival (PFS)**

Median progression free survival (PFS) will be measured using imaging by MRI scan and evaluated by RECIST v1.1, mRECIST, and volumetrically (change in tumor volume as assessed by MRI volumetric).

Progression-free survival is defined as the time from start of treatment to date of progression or death due to any cause. If a subject is not known to have progressed or died, then PFS will be censored at the latest date the subject was known to be alive or progression-free (on or before the cut-off date). The PFS distribution will be estimated using the Kaplan-Meier method, and

the Kaplan-Meier curves, medians and 95% confidence intervals of the medians will be presented.

10.2.2.3. **Objective Response Rate (ORR) at 1 year**

For the objective response rate (ORR) at 1 year, the percentage of subjects who start study treatment and achieve an objective response (CR or PR) will be calculated. ORR will be measured using imaging by MRI scan and evaluated both RECIST v1.1, mRECIST, and MRI volumetric.

The ORR will be calculated as the proportion of subjects with objective response. The ORR and the two-sided 95% Clopper-Pearson (exact) confidence interval will be calculated.

10.2.2.4. **Time to Response (TTR)**

Time to response is defined as the time from the start of treatment with nirogacestat to the first objective tumor response (CR or PR), and will be measured using imaging by MRI scan and evaluated by RECIST v1.1, mRECIST, and volumetrically.

The TTR distribution will be estimated using the Kaplan-Meier method, and the Kaplan-Meier curves, medians and 95% confidence intervals of the medians will be presented.

10.2.2.5. **Duration of Response (DoR)**

Duration of response (DoR) is defined as the time from the date of documented disease response (CR or PR) to the date of the first documented progression, and will be determined using imaging by MRI scan and evaluated by RECIST v1.1, mRECIST, and volumetrically.

Duration of response will be summarized descriptively. If sufficient data are available the distribution will be estimated using the Kaplan-Meier method, and the Kaplan-Meier curves, medians and 95% confidence intervals of the medians will be presented.

Nominal duration of study involvement is 26 months, with last assessment after about 24 months of treatment.

10.2.2.6. **Adverse events and safety**

Adverse events will be tabulated with frequencies and percentages for grade, severity, status and relationship to study drug or study procedure. The analysis population will include all subjects who have started study treatment. Assessment for safety signals will be from time of consent until 30 days after the last treatment.

10.2.3. **Exploratory Endpoints and Analysis**

10.2.3.1. **Patient-reported outcomes (EQ-5D-3L)**

Summary measures (mean, standard deviation, median, interquartile range) of the EQ-5D-3L survey scores will be calculated for each time point during the duration of the study; scores will graphically depicted at each time point. In addition, we will calculate the difference of the scores at the baseline, time of demonstrated clinical benefit rate, and last follow-up date and report summary statistics. Nominal duration of study involvement is 26 months, with last assessment after about 24 months of treatment.

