2.1.4. Scientific Justification for Study Design

This is a phase 2 study evaluating the addition of a drug (nirogacestat) that has single agent activity, to cryoablation, a well-established therapy for both first-line or salvage treatment of desmoid tumor.

Clinical Benefit Rate at 1 year is chosen as the primary endpoint because this endpoint measures the effect of combining the two modalities of local cryoablation with systemic targeted therapy. The one-year timepoint for assessments was chosen because maintaining response or not progressing from stable disease for 1 year is clinically meaningful for subjects with desmoid tumors. We will also be assessing quality of life (QoL) outcomes to determine if subjects symptomatically benefited from treatment.

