2.3.2. Outcome Measures for ClinicalTrials.gov Results Reporting

2.3.2.1. Primary Outcome

- **Primary Outcome Measure Title:** Clinical Benefit per RECIST v1.1

Description: Clinical benefit (CB) is defined as the number of participants assessed with a complete response (CR), partial response (PR), or stable disease (SD) within 1 year and with no evidence of loss of response nor progression within that year.

Response & progression will be assessed according to the Revised Response Evaluation Criteria in Solid Tumors (RECIST)v1.1, as follows:

RECIST v1.1:

- CR=Disappearance of all lesions
- PR= $\geq 30\%$ decrease in diameter of target lesions
- Progressive disease (PD)=20% increase in diameter of target lesion; progression of non-target lesion; or ≥ 1 new lesion(s)

For the overall outcome:

- SD=Changes not meeting above criteria
- Overall Response (OR)=CR+PR
- CB=CR+PR+SD

The outcome is a number without dispersion.

- **Time Frame:** 1 year
- **Completion of Primary Outcome:** Based on the projected accrual of 20 subjects within 24 months, the last datum for the primary objective / outcome is expected to be obtained approximately 44 months from the time the study opens to accrual.

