2.3.2.2. Secondary Outcomes

- **Outcome 2 (Secondary) Title:** Clinical Benefit per mRECIST

Description: Clinical benefit (CB) is defined as the number of participants assessed with a complete response (CR), partial response (PR), or stable disease (SD) within 1 year and with no evidence of loss of response nor progression within that year.

Response & progression will be assessed according to the modified Revised Response Evaluation Criteria in Solid Tumors (mRECIST), as follows.

mRECIST:

- CR=Disappearance of intratumoral enhancement
- PR= $\geq 30\%$ decrease in the diameter of target lesion(s)
- PD=An increase of $>20\%$ in the diameter of target lesion.

The outcome is the number of participants alive after 1 year and without PD per mRECIST, a number without dispersion.

Time Frame: 1 year

- **Outcome 3 (Secondary) Title:** Progression-free Survival (PFS)

Description: Progressive-free survival (PFS) is an assessment of the number of participants at a specific time who remain alive and without tumor progression.

Progressive disease (PD) will be assessed according to Revised Response Evaluation Criteria in Solid Tumors (RECIST)v1.1, or, for tumors assessed with MRI enhancement, modified RECIST (mRECIST) defined as follows:

RECIST v1.1:

- PD=20% increase in diameter of target lesion; progression of non-target lesion; or ≥ 1 new lesion(s)

mRECIST:

- PD=An increase of $>20\%$ in the diameter of target lesion.

The outcome is the number of participants alive after 1 year and without PD per RECIST or mRECIST, a number without dispersion.

Time Frame: 1 year

- **Outcome 4 (Secondary) Title:** Objective Response

Description: Objective response (OR) is defined as the number of participants assessed with a complete response (CR) or partial response (PR) within 1 year and with no evidence of loss of response nor progression within that year. Response & progression will be assessed according to the Revised Response Evaluation Criteria in Solid Tumors (RECIST)v1.1, or, for assessed with MRI enhancement, modified RECIST (mRECIST) as follows:

RECIST v1.1:

- CR=Disappearance of all lesions
- PR= $\geq 30\%$ decrease in diameter of target lesions
- Progressive disease (PD)=20% increase in diameter of target lesion; progression of non-target lesion; or ≥ 1 new lesion(s)

mRECIST:

- CR=Disappearance of intratumoral enhancement
- PR= $\geq 30\%$ decrease in the diameter of target lesion(s)
- PD=An increase of $>20\%$ in the diameter of target lesion.

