2.3.1. Evaluation of target lesions

Complete Response (CR): Disappearance of all target lesions. Any pathological lymph nodes (whether target or non-target) must have reduction in short axis to < 10 mm.

Partial Response (PR): At least a 30% decrease in the sum of diameters of target lesions, taking as reference the baseline sum diameters.

Progressive Disease (PD): At least a 20% increase in the sum of diameters of target lesions, taking as reference the smallest sum on study (this includes the baseline sum if that is the smallest on study). In addition to the relative increase of 20%, the sum must also demonstrate an absolute increase of at least 5 mm. (Note: the appearance of one or more new lesions is also considered progression).

Stable Disease (SD): Neither sufficient shrinkage to qualify for PR nor sufficient increase to qualify for PD, taking as reference the smallest sum diameters while on study.

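### The primary endpoint adds an undefined loss-of-response failure that penalises a PR-to-SD subject, while the primary analysis rule counts that subject as a success

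*Protocol*

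**What the plan says.** Section 10.2.1.1 defines clinical benefit as being "assessed with either a complete response (CR), a partial response (PR), or stable disease (SD) prior to 1 year after treatment start", with the added condition that subjects "show no evidence of loss of response nor progression" within the year. Outcome 1 in section 2.3.2.1 repeats the condition: "with no evidence of loss of response nor progression within that year". It then closes by setting clinical benefit equal to CR + PR + SD.

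Section 10.2.1.2, the primary analysis plan, gives a different rule. It counts subjects "who achieve a complete response (CR), partial response (PR), or stable disease (SD) as measured at 12 months" (± 1 month) and has no loss-of-response condition.

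Outcome 2 in section 2.3.2.2 (clinical benefit by mRECIST) carries the condition in its description but ends with another rule: "The outcome is the number of participants alive after 1 year and without PD per mRECIST".

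The rationale in section 2.1.4 says that "maintaining response or not progressing from stable disease for 1 year is clinically meaningful".

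Appendix C, section 2.3.1, defines PR as "At least a 30% decrease in the sum of diameters of target lesions, taking as reference the baseline sum diameters". It defines SD as "Neither sufficient shrinkage to qualify for PR nor sufficient increase to qualify for PD". Progression there is a rise of at least 20%, and at least 5 mm, from the smallest sum on study.

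**The concern.** Section 10.2.1.1 names loss of response and progression as two separate things, so on a plain reading the first is a failure route of its own. A responder who drifts back above the PR threshold without progressing is SD by Appendix C, and SD is a qualifying state. The condition therefore holds responders to a stricter standard than subjects who never respond, and can rank a smaller tumour below a larger one.

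Three features make this matter in practice. Response needs no confirmation (Appendix C, section 2.4.3), so one reading at the threshold can create a response that is later lost. The treating investigator determines response in an open-label trial (section 10.2.1.4). And the 50% null rests on recurrence at 1 year (section 10.4.3), which does not describe a lapse from PR to SD. With 20 subjects, the choice between two success rules after the scans are read could decide the result.

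**Working it through.** **Inputs.** RECIST thresholds are from Appendix C, section 2.3.1. N = 20, null 0.5, alternative 0.8, one-sided exact alpha 0.05 and stated power 100.0% are from section 10.4.2. The cut-off of 11 or more successes is from section 10.4.4. The share of subjects going from PR to SD without progression is not in the documents and is assumed below.

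**1. Can a PR become SD without progression?** Take a baseline sum of 100 mm and a smallest later sum *s*.

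- PR requires *s* ≤ 70 mm, and is lost once the sum exceeds 70 mm.
- Progression requires a sum of at least 1.2 × *s*.
- There is room between the two only if 1.2 × *s* > 70, so *s* > 70/1.2 = 58.3 mm.

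The path is open for 58.3 < *s* ≤ 70 mm, which is a nadir about 30% to 41.7% below baseline. At a deeper nadir, progression is reached no later than the PR threshold is crossed, so the subject fails with or without the condition. The 5 mm floor changes this only for small lesions.

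**2. Two subjects under the protocol's rules.**

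- Subject A: 100, 65, 73 mm. At 65 mm the change from baseline is −35%, so PR. At 73 mm it is −27% from baseline and 73/65 − 1 = +12.3% from the smallest sum, so SD and not progression.
- Subject B: 100, 115 mm. The change is +15% from the smallest sum (baseline), so SD throughout.

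| Rule | A | B |
|---|---|---|
| 10.2.1.1 and the description of Outcome 1 | fails on the plain reading | passes |
| 10.2.1.2, with the last value as the 12-month scan | passes | passes |
| Closing sentence of Outcome 2, with the sums read as enhancing diameters | passes | passes |

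A's tumour is 73 mm and B's is 115 mm, yet only A can fail.

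**3. The protocol's power figure.** With X ~ Bin(20, p), power is P(X ≥ c) at p = 0.8. The smallest cut-off with P(X ≥ c) ≤ 0.05 at p = 0.5 is c = 15 (exact alpha 0.0207; c = 14 gives 0.0577), and its power is 80.4%. The stated 100.0% is not reproduced there. The protocol's c = 11 comes closest at 99.7%, with exact alpha 0.412. That is a separate problem, but it means both cut-offs should be shown.

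**4. Illustrative cost of the condition.** One subject in 20 is 1/20 = 5 points of CBR. Assume the planned 80% is the rate without the condition, and subtract 0, 5 or 10 points.

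| Points lost | p | P(X ≥ 15) | P(X ≥ 11) |
|---|---|---|---|
| 0 | 0.80 | 80.4% | 99.7% |
| 5 | 0.75 | 61.7% | 98.6% |
| 10 | 0.70 | 41.6% | 95.2% |

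**The case against.** The best reply is that loss of response is never defined and may mean no more than progression. Duration of response (section 10.2.2.5) ends only at progression, and the closing sentence of Outcome 2 turns the same condition into survival without progression. The analysis plan in 10.2.1.2, the synopsis and the primary objective have no such condition, so if 10.2.1.2 governs, neither the CBR nor the power is reduced. This stands as a limit: the documents do not show that the stricter rule will be applied. It does not remove the conflict. If the phrase means progression, it is redundant. If 10.2.1.2 governs, 10.2.1.1 and the registry outcome state the wrong rule.

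A second reply is that section 2.1.4 makes the asymmetry deliberate. That may be so, but it then contradicts 10.2.1.2 and Outcome 2, and the term still needs a definition.

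A reader might also infer more than the documents support:

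- That the penalty grows with treatment activity. It does not follow, because deeper responses leave the affected window (step 1).
- That a large share of responders would be lost to reading error. Assuming a true shrinkage of 32% to 33% and a reading SD of 3 to 5 points, the chance that at least one of the next two scans falls short of −30% is 29% to 57%. At a true 40% with the same SDs it is 0.1% to 4.5%. The documents give neither quantity.
- That about 8 of 20 subjects would be responders at risk. This takes the 41% phase 3 ORR from section 1.2.4. The protocol's own 1-year figure for nirogacestat alone is 2 of 17 (12%, section 1.1), or about 2 of 20.

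**Conclusion.** The concern holds as a conflict of definitions. On its plain wording, section 10.2.1.1 fails a subject who moves from PR to SD without progression, while 10.2.1.2 and the closing sentence of Outcome 2 count such a subject as a success. The wording also ranks some better outcomes below worse ones. This follows from the protocol's own RECIST thresholds and needs no assumption about frequency.

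The effect is confined to nadirs of about 30% to 41.7% below baseline. The number of affected subjects cannot be derived from the documents. The power figures in step 4 are illustrations. They rest on the assumed 5 or 10 points, on the stricter rule being applied, and on the planned 80% excluding it. The large drop also depends on the cut-off of 15, which is not the protocol's.

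**What to change.** Delete the loss-of-response condition from section 10.2.1.1 and from Outcomes 1 and 2 in section 2.3.2, so that failure within the year is progression (RECIST v1.1 for the primary endpoint, mRECIST for Outcome 2) or death. State the same single rule in 10.2.1.2, for example: CR, PR or SD at the 12-month (± 1 month) assessment, with no progression and no death from treatment start up to that assessment. This also settles whether benefit is judged through the year or only at 12 months, which deletion alone would leave open. Bring the rationale in 2.1.4 into line. A durable-response condition can stay in Outcome 4 (objective response). Make the change before any primary outcome is scored.

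The cost is a wording amendment to the protocol and the registry entry. The primary endpoint also loses the response-maintenance element that 2.1.4 mentions, which duration of response still captures in part.

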**Continued Treatment with Nirogacestat (Cycle 4 onwards)**

Maximum duration of treatment with nirogacestat via this study is 24 months (26 cycles of treatment).

(Routine labs and urine pregnancy test, every cycle for Cycle 4 (C4) through Cycle 6 (C6), then every 3 cycles [ie, C9, C12, C15, C18, C21, C24])

(EQ-5D-3L questionnaire every cycle for Cycles 5 through 9, then every 3 cycles [ie, C12, C15, C18, C21, C24]. There will not be a questionnaire for Cycle 4. For those cycles where subjects are not having an in-person visit (C7 & C8), the EQ-5D-3L questionnaire will be sent to subjects via secure Email or MyHealth Epic message for completion and return via secure Email or MyHealth Epic message).

(Physical exam, vital signs, weight, performance status evaluation, AE and concomitant medication review every cycle for C4 through C6, then every 3 cycles [C9, C12, C15, C18, C21, C24])

(Radiologic imaging [MRI] every 3 cycles = every 12 weeks \pm 14 days (i.e., Before C7, C10, C13, C16, C19, C22, C25)).

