1.1. Study Rationale

In this trial, we propose the combination of systemic therapy with nirogacestat and cryoablation to maximize the benefits of both modalities for subjects with growing or symptomatic desmoid tumors. It is hypothesized that the combination will provide long-lasting disease control and a quick time to treatment response.

This phase 2 study will enroll participants \geq 18 years of age. The pharmacokinetics (PK) and optimal dosing of nirogacestat in younger participants has not been established.

Treatment will consist of a 3-month lead-in period of nirogacestat, followed by cryoablation procedure (single treatment), followed by continued nirogacestat treatment for up to a total of 24 months (maximum 26 cycles of treatment), unless disease progression or one of the criteria in Section 3.7 (Subject Study Completion or Termination) occurs. The lead-in period will allow assessment of the response to nirogacestat-alone and potentially lead to improved cryoablation success if there is tumor shrinkage.

In order to assess increased efficacy of combination therapy over single-modality cryoablation, results will be compared to historical data from the Stanford existing cryoablation population treated at Stanford. For these subjects, two-thirds are unable to be completely ablated and most of those patients will have clearly recurrent disease at 6 months. Therefore, we hypothesize that adding on nirogacestat to cryoablation will lead to an 80% clinical benefit rate at 1 year.

Nirogacestat alone has a RECIST response of 29% of patients at a median of 24 months.¹ At 1 year, the ORR was 2 of 17 (12%).

To evaluate effects of cryoablation plus nirogacestat on quality of life (QOL), we will collect patient-reported outcome (PRO) measures using the EQ-5D-3L.

To remain consistent with prior inclusion criteria for desmoid trials, we will only include subjects with growing or symptomatic desmoid tumors. In addition, we will standardize the cryoablation procedure by limiting subjects to 1 cryoablation treatment session at time of intervention and desmoid tumors that can be at least 50% treated with cryoablation but are $<$ 75% cryoablitable.

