3.5. Treatment Period and Duration

Treatment may continue via this study protocol for up to 24 months (26 cycles of treatment), unless there is progression of disease, intolerance, start of new anticancer therapy (as defined in Section 5.7.2.), or one of the criteria in Section 3.7 (Subject Study Completion or Termination) occurs. After 24 months of treatment, if clinically indicated, a subject may transition to commercial nirogacestat supply, once the subject has completed the End of Treatment (EOT) visit and is off study.

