3.5.2. Definition of Off-treatment

The subject is considered to be off-treatment when the subject is no longer receiving the study agent.

In the absence of treatment delays due to an adverse event(s), treatment may continue with 3 cycles of nirogacestat (1 cycle = 28 days), followed by 1 session of cryoablation in between Cycles 3 and 4 of nirogacestat, followed by continued treatment with nirogacestat alone for Cycles 4 through 26, unless there is disease progression, unacceptable side effects, start of new anticancer therapy (as defined in Section 5.7.2), or until one of the criteria in Section 3.7 occurs.

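### Section 10.2.1.2 reads 1-year clinical benefit in a window that a compliant pre-Cycle 13 MRI can miss, and it drops the no-loss, no-progression condition of Sections 10.2.1.1 and 2.3.2.1

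*Protocol*

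**What the plan says.** Section 10.2.1.2 defines the primary clinical benefit rate (CBR) as the percentage of subjects "who achieve a complete response (CR), partial response (PR), or stable disease (SD) as measured at 12 months", with a tolerance of one month either side, counted from the start of treatment. It adds no condition about the course of disease before that point.

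Two other sections define the same endpoint with such a condition. Section 10.2.1.1 requires subjects to be assessed with CR, PR or SD "prior to 1 year after treatment start and show no evidence of loss of response nor progression" within that year. The registry outcome in Section 2.3.2.1 asks for the same thing: "within 1 year and with no evidence of loss of response nor progression within that year".

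MRI is every 3 cycles, equated with every 12 weeks, with a tolerance of 14 days (Sections 6.1 and 10.2.1.5). The Protocol Schema places the scans after Cycle 4 "Before C7, C10, C13, C16, C19, C22, C25". A cycle is 28 days (Section 5.3).

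Months are used in two ways. Section 3.5 lets treatment run for "up to 24 months (26 cycles of treatment"), which is a calendar-length month. Section 1.1 calls the first three cycles a "3-month lead-in period of nirogacestat", and Section 10.5 equates three months with three cycles in the same way.

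**The concern.** The primary analysis has its own read-out window, and the imaging schedule has its own tolerance. If the two do not match, a scan that complies with the schedule may lie outside the window in which the endpoint is read, with no other scheduled scan to take its place. The protocol does not say which scan is the 1-year scan.

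Separately, the primary endpoint is defined in three places and the definitions are not the same. Section 10.4.4 draws the trial's conclusion from a count of responses in 20 subjects. The study is open-label and the treating investigator determines response (Section 10.2.1.4). A choice between definitions, or about an out-of-window scan, should therefore be made before outcome data are read.

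**Working it through.** **Window against schedule** (days counted from treatment start, tolerances from the nominal date, cycles on schedule)

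1. The plan's own figures reproduce: 3 × 28 = 84 days = 12 weeks, and 26 × 28 = 728 days. Section 3.5 then gives 728 / 24 = 30.33 days per month.
2. Scan ranges, nominal date ± 14 days:
   - before Cycle 10: 9 × 28 = 252, so days 238 to 266
   - before Cycle 13: 12 × 28 = 336, so days 322 to 350 (29 permitted days)
   - before Cycle 16: 15 × 28 = 420, so days 406 to 434
3. The window is 11 to 13 months. Its edges depend on the length of a month:

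| Month taken as | Window (days) | Permitted days of the Cycle 13 scan before opening |
|---|---|---|
| 30.33 days (26 cycles = 24 months) | 333.7 to 394.3 | 12 of 29 (322 to 333) |
| 365.25 / 12 days | 334.8 to 395.7 | 13 of 29 (322 to 334) |
| 30 days | 330 to 390 | 8 of 29 (322 to 329) |
| 28 days (one cycle) | 308 to 364 | 0 of 29 |

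4. On every row the Cycle 10 scan ends before the window opens and the Cycle 16 scan starts after it closes. The Cycle 13 scan is the only scheduled one that can fall inside, and its nominal day 336 is always inside. On the two calendar-length rows it is only 1 to 2 days past the opening.
5. Delay: if cycles have slipped by 7 days in total, the Cycle 13 range becomes days 329 to 357, and 5 to 6 of 29 days precede an opening at day 334 or 335. A slip of 12 to 13 days leaves none.

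**The omitted condition**

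1. Under Appendix C, PR needs a sum of diameters at least 30% below baseline. PD needs an increase of at least 20%, and at least 5 mm, over the smallest sum on study. Anything between is SD.
2. Take sums of 100, 68 and 76 mm. At 68 mm the change from baseline is −32%, so PR. At 76 mm it is −24%, no longer PR. Against the smallest sum, (76 − 68) / 68 = 11.8%, below 20%, so not PD. The reading is SD.
3. Section 10.2.1.2 counts this subject as benefit. On the plain words about loss of response, Sections 10.2.1.1 and 2.3.2.1 may not.
4. How far this can reach: with baseline sum b and smallest sum n, PR can revert to SD without PD when n ≤ 0.70b and 1.2n > 0.70b. That is a best shrinkage of 30% to under 41.7%, for baseline sums of about 43 mm or more. Below that the 5 mm rule raises the upper bound to 30% + 5/b, for example 46.7% at 30 mm and 55% at 20 mm.
5. Each reclassified subject moves CBR by 1/20 = 5 percentage points.

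**The case against.** On the window, the protocol gives no day numbers, and its use of months is mixed. On the usage in Sections 1.1 and 10.5 the whole Cycle 13 range is inside. Delays are foreseeable: Section 3.5.2 describes the schedule "In the absence of treatment delays due to an adverse event(s"), and cryoablation sits between Cycles 3 and 4. Both points stand, and they are why the exclusion is conditional. The 28-day month, however, fits poorly with Section 3.5 and with the gloss in Section 10.2.1.2 that the time point is roughly one year.

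A reader might go further and infer that 41 to 45% of subjects, or 8 to 9 of 20, would have no usable 1-year scan. That needs scan dates spread evenly over the permitted range, which nothing in the document supports. Nor does the document say that a scan before the window opens is missing or a failure; that rule may be in the SAP.

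On the definition, Section 10.2.1.2 can be read as only adding timing to an endpoint already defined in Section 10.2.1.1. Yet it defines CBR afresh, so the texts differ as written. The better counter-argument is that the protocol leans towards progression as the event that ends a response. Section 10.2.2.5 runs duration of response to first documented progression. Outcome 2 in Section 2.3.2.2 uses the same sentence about loss of response and then states: "The outcome is the number of participants alive after 1 year and without PD per mRECIST". This is good evidence but not conclusive, because Section 2.1.4 justifies the endpoint partly by the value of keeping a response for a year.

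The practical reach is also modest. Progression is itself a stated reason to end treatment, so the gap is mainly PR reverting to SD. Section 1.1 gives a 1-year response rate of only 2 of 17 (12%) for nirogacestat alone, though the combination may do better. A single reclassified subject changes the conclusion only when the count is at the cut-off.

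**Conclusion.** Both points hold as inconsistencies in stated text, in limited form.

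- **Window.** A compliant pre-Cycle 13 MRI can miss the primary read-out window, but need not. The size is 12 to 13 of 29 permitted days. This assumes on-schedule cycles, calendar-length months and tolerances counted from treatment start. It is zero with 28-day months or after a slip of about 13 days. A discretionary end-of-treatment or unscheduled scan could also fall in the window. The number of subjects affected cannot be derived from the protocol.
- **Definition.** Section 10.2.1.2 lacks a condition that Sections 10.2.1.1 and 2.3.2.1 share. The difference bears on PR that returns to SD without PD, at 5 points of CBR per subject. It does not depend on month length or delay. It would be too strong to say that such a subject is certainly a failure under the other two sections, because the protocol's own usage leans towards a progression-based reading without settling it.

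This is worth correcting before outcome data are read. It does not show that the primary result will be wrong.

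**What to change.** In Section 10.2.1.2, name the scheduled pre-Cycle 13 MRI as the 1-year assessment, at any date its imaging tolerance permits (from day 322), and keep the 13-month upper limit.

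Use one CBR definition in Sections 2.3.2.1, 10.2.1.1 and 10.2.1.2: CR, PR or SD by RECIST v1.1 on that MRI, with no PD at or before it. Replace the loss-of-response wording with this. If the sponsor instead intends PR returning to SD to be a failure, all three sections should say so before outcome data are read. Either way, report the count under the other rule as a sensitivity analysis.

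The cost is wording in three sections, with no added scan or visit. An upper limit of day 395 holds the whole Cycle 13 range for cumulative cycle slips of up to 395 − 350 = 45 days (43 if 13 months is as short as 393 days). It stops short of the on-schedule Cycle 16 scan at day 406. The small downside is that the landmark may be read as early as week 46 (322 / 7), 365 − 322 = 43 days before a full year. Progression between that scan and day 365 would then not be seen until the Cycle 16 scan.
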